#### Intervention

After two months, the researcher will visit the home to install the equipment. A camera and microphone will be placed on a pole, secured between floor and ceiling, next to the subject's bed. A suitcase containing a MacBook laptop and an external hard drive for data storage will be placed in the subject's room. The subject will be instructed to wear the NightWatch bracelet every night around the upper arm. When NightWatch is removed from its docking station, it will start running automatically. All recorded data (NightWatch, video and audio) will be stored automatically to the

MacBook and copied on hard drive. The researchers will replace the hard-drive every 2 weeks and store all recordings safely at SEIN or Kempenhaeghe for analysis. During the first weeks, the hard drive will be switched more often, in order to detect systematic errors in time.

In the morning, NightWatch must be connected to the docking station, when this happens, recordings stop automatically. During the study, subjects (or parent(s)/guardian(s)) do not have to switch any on/off button for the recordings. When NightWatch detects a seizure, it generates an alarm to the alarm station part of the NightWatch system at the parent(s)/guardian(s) bedroom. When the alarm goes off, the responding parent/guardian will check on their child and act upon the situation. He/she will keep a diary of all events. The SDD intervention period will last two months.

In case of technical problems, parent(s)/guardian(s) can contact the technical trial coordinator. If the parent(s)/guardian(s) give their consent, the coordinating investigator will be able to look into the study Macbook at their home from a distance true a secured program to solve technical problems. If the problem is not solved, the technical trial coordinator will visit the participant's home.

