#### 1. INTRODUCTION AND RATIONALE

Epilepsy impacts ~180.000 people in the Netherlands [1]. Despite advances in treatment, one third of all people with epilepsy continue to have seizures [2] that adversely affect quality of life (QoL) [3,4]. Poor seizure control is the major determinant of impaired QoL. Seizures impact not only individuals with epilepsy but also their guardians [5-7] as seizures are (1) unpredictable, (2) may cause loss of control and (3) cause life threatening situations, including injuries, status epilepticus and sudden unexpected death in epilepsy [8]. Convulsive seizures carry the greatest mortality risk, particularly those occurring at night, as these are often unwitnessed [9]. Childhood epilepsy has also a severe impact on parental QoL [10] and monitoring devices can help to improve parental anxiety levels, quality of sleep, and QoL [11]. Various non-EEG based signals have been assessed for the detection of potentially dangerous seizures [12]. Seizure detection devices (SDDs) have had, however, limited impact on epilepsy care so far. Barriers to SDD implementation include lack of external validation and high rate of false alarms. Most SDDs rely on a single modality. This approach likely explains limited sensitivity and specificity [12]. Previous studies validated multimodal algorithms for wearable sensors (accelerometry & heart rate) and demonstrated the feasibility of remote sensors (audio & video) to detect seizures [13-17]. Preliminary results indicate that the performance of the NightWatch is superior to a commonly used bed sensor, the Emfit. Our multicenter prospective trial in a residential population of adults with epilepsy and learning disabilities (LICSENSE trial, NTR4115) shows a median sensitivity per person of 85.7% with a positive predictive value of 49.3% and a median false negative alarm rate of 0.04 per person per night [18]. The interim analysis of our recent trial in 21 children (LICSENSE phase III) indicated that the algorithms needed an adjustment as in children higher heart rates are more common and less specific features for epilepsy appear thus increasing the number of false alarms. In response we updated our algorithm (with less emphasis on heart rate changes and more weight on movement changes). This approach still reach 80% sensitivity and 50% PPV in the majority (80%) of subjects (adults and children). This current prospective home-based trial is needed as a final validation step for the new algorithm in children and to evaluate feasibility of NightWatch. Former trials were performed without actual alarms. The current trial also enables us to get insight in the real life situation of children and their parents/guardians by focusing on feasibility. The literature has so far only discussed these needs with questionnaires but without insight into the home situation [19].

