#### 3. STUDY DESIGN

This is a home-based medical device intervention study, with prospective validation of our wearable device, including 60 children with refractory epilepsy (≥1 major nocturnal seizure per week) from three epilepsy centers (SEIN, Kempenhaeghe, UMCU). Subjects will receive usual care during the first two months (non-exposure period), followed by home-based nocturnal monitoring for two months (exposure period) [See Figure 1]. In both periods parents/guardians will be invited to keep a seizure diary. The NightWatch wirelessly transmits sensor outputs to a monitor in the parents/guardians room to alert them in case of a suspected seizure [See Figure 2]. Simultaneous video and audio recordings will be stored and analyzed offline.[21] Both algorithms will generate marks in dataflow, but these marks will not be used to alert the parents/guardians and will only be examined by the researchers.[See figure 3] The video material will also be used to screen for false negative alarms and to improve the algorithm when necessary (comparable with the LICSENSE study design, NTR4115).

Trial nurses will check the validity of the generated alarms and marks in a blinded way and screen 5% of the nocturnal video recordings without alarms. The LICSENSE trial demonstrated a median false negative alarm rate (FNAR) of 0,03 per subject per night with 10% screening of all nights. We believe that 5% screening will also be feasible, but we will perform an interim analysis after inclusion of 20 subjects to see whether FANR is still reasonably low (below 0,1 per night). If this is not the case, we will increase screening to 10% of all nights. The LICSENSE trial found a high Cohen's kappa (0.77) for inter-observer agreement between trial nurses and neurologists. Therefore, this expert review of the nocturnal video recordings by the trial nurses will serve as the gold standard. Cases of doubt will be discussed with a neurologist. Seizures will be stratified according to type (tonic-clonic, >30 seconds tonic, hyper motor and major) and severity (minor/major).

Parents/guardians will be invited to articulate their user experiences at focus meetings. Video tracings of detected seizures of their child will be shown to the parents/guardians who will be asked to indicate whether they would want to be alerted for these events or not. Results from these meetings will be included in the discussion on which type of seizures should be alarmed by SDDs.

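### Remote video/audio performance is scored on footage that contains parent visits triggered by NightWatch, and the plan has no rule for those periods

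*Combined protocol and SAP*

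**What the plan says.** Section 8.3 (Intervention) describes the live alarm. When NightWatch detects a seizure, "it generates an alarm to the alarm station part of the NightWatch system at the parent(s)/guardian(s) bedroom". Then: "When the alarm goes off, the responding parent/guardian will check on their child and act upon the situation". The recording equipment is at the bedside: "A camera and microphone will be placed on a pole, secured between floor and ceiling, next to the subject's bed". Recording ends only when NightWatch is docked in the morning.

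Section 3 puts the remote system on the same nights: "Simultaneous video and audio recordings will be stored and analyzed offline". Its output is silent: "these marks will not be used to alert the parents/guardians and will only be examined by the researchers". These marks feed the sensitivity, positive predictive value (PPV) and false alarm rate of the remote system, a secondary objective (sections 2 and 8.1.2).

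On review, section 3 says: "Trial nurses will check the validity of the generated alarms and marks in a blinded way". The nurses' video review is the gold standard. How the blinding is achieved is not described. Section 8.2, whose heading covers randomisation, blinding and allocation, is marked not applicable.

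Section 1 notes: "Former trials were performed without actual alarms". Sections 10.1 and 10.2 set no rule for periods when a parent is at the bedside; section 10.1 promises descriptive statistics only.

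**The concern.** The two systems are tested in the same room on the same nights, and one of them changes what the other records. After a false NightWatch alarm, the footage shows an adult entering, moving and touching the child. If the video algorithm marks this, it counts as a remote false alarm. After a true alarm, a mark caused by the parent could be credited as a remote detection of the seizure. The remote result would then depend partly on how often NightWatch alarms. Section 1 proposes the remote system as an alternative where a wearable is not tolerated. In that use there would be no NightWatch-triggered visits. Section 1 also says that long recordings are needed to establish the remote false alarm rates, so this is a quantity the study is meant to deliver.

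The second strand concerns the reference standard. A parent appearing soon after an event may suggest to the nurse that NightWatch alarmed. The agreement figure that supports nurse review (kappa 0.77, section 3) comes from a trial without live alarms, so it does not cover footage with alarm-triggered visits.

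**Working it through.** **Inputs from the documents.** 60 children, two months, at least one seizure per week, around 540 seizures, target sensitivity 80% and PPV 50% (section 4.4). Earlier video false detection rate: median 0.78 per night. Earlier audio false alarm rate: mean 1.29 per night (both section 1).

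**Assumptions.** 60 monitored nights per child, every alarm answered, and a fraction *q* of false-alarm visits triggering one remote mark. The documents give no value for *q*.

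**Plan's own figure.** 60 children × 9 weeks × 1 per week = 540 seizures, which reproduces section 4.4.

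**Expected visits.**
- True alarms: 540 × 0.80 = 432.
- All alarms: 432 / 0.50 = 864, so false alarms: 864 − 432 = 432.
- Nights: 60 × 60 = 3,600.
- Visits per night: 864 / 3,600 = 0.24, of which 432 / 3,600 = 0.12 follow false alarms.

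The 540 rests on the minimum seizure frequency. At the same PPV, more seizures would raise the number of visits in proportion.

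**Effect on the remote false alarm rate.** Only visits after false NightWatch alarms are used here. Added marks per night = 0.12 × *q*.

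| *q* | Added per night | Video, relative to 0.78 | Audio, relative to 1.29 |
|---|---|---|---|
| 0.1 | 0.012 | +1.5% | +0.9% |
| 0.5 | 0.06 | +7.7% | +4.7% |
| 1 | 0.12 | +15.4% | +9.3% |

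The percentages are indicative. The 0.78 is a median from a small clinical cohort, and an expected mean is being added to it. The audio column is an upper limit for each *q*, because section 11.6 removes audio fragments that could identify the child, such as speech, from the audio company's analysis.

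**Effect on remote sensitivity.** On the targets, 432 of 540 seizures (80%) would bring a NightWatch-triggered visit. Only seizures whose first remote mark comes after the NightWatch alarm can be affected. The documents give no basis for estimating that number.

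**The case against.** Several counter-arguments are fair.

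- **Silence is not a counting rule.** The plan does not say that marks made during visits are counted. The analysis is offline, so they could still be excluded. This stands: the gap is a missing rule, not a stated error.
- **Visits also occur in real use.** A remote system that alerted would itself bring a parent to the bed, and section 4.3 permits a baby phone, so parents may enter for other reasons. This stands for visits during true seizures. It does not cover visits caused by false NightWatch alarms.
- **Audio is partly protected.** The speech rule in section 11.6 helps, although it is a privacy measure and leaves video and non-speech sound untouched. Section 1 also attributes all earlier audio false positives to minor seizures.
- **The endpoint is secondary**, and section 1 says the remote algorithms are to be optimised in this study. That lowers the weight of the point. It does not make an avoidable dependence between devices harmless, since the same footage would be used for the optimisation.

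A reader might go further and infer that the blinded review is undone. The documents do not support this. A nurse judging flagged clips already knows that some device flagged them. Entry can at most hint at which one, and section 11.4 allows audible alarms to be switched off. The blinding method is undescribed, which is not the same as absent.

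A reader might also take all 0.24 visits per night against 0.78 and report an inflation of 31%. That mixes in visits during true seizures, where a mark is not a false alarm, and assumes that every visit triggers a mark.

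Nor do the documents show that the whole design was carried over from the earlier trial. The comparison in section 3 concerns the use of video to screen for missed seizures and improve the algorithm. No statement says that caregivers never entered the room in earlier trials.

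**Conclusion.** The point holds in a limited form. The protocol sends a parent into a room that is still being recorded, in response to one device, and scores the other device on that footage without a rule for those periods. If all marks are scored, the remote video false alarm rate can be inflated by roughly 1.5% to 15% of the earlier rate for *q* from 0.1 to 1, and less if alarms go unanswered. The effect on audio is smaller. Remote sensitivity may be blurred by an amount that cannot be computed from the documents.

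For the nurse review, visible entry is a possible but imperfect cue. I put no size on its effect on NightWatch sensitivity or PPV, because nothing in the documents supports one. The change is worth making because it is cheap and removes a dependence between the two devices.

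**What to change.** **Section 10.2.** Pre-specify that remote sensitivity, PPV and false alarm rate are reported twice: on all footage, and after excluding marks and recording time in a fixed window following each NightWatch alarm. Use the stored alarm times, and fix the window length before annotation starts. For sensitivity, also report whether each remote mark came before or after the NightWatch alarm, and keep late detections in the all-footage result. Crediting only marks that precede the parent's entry would discard genuine detections: section 1 gives 67% of earlier video latencies as 10 seconds or less, so 33% were longer. Restricting the analysis to footage with no adult present would require presence to be annotated on all nights, whereas nurses screen only 5% of recordings without alarms.

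**Section 3.** State how the blinding works, withhold from the nurse which device flagged each clip, and acknowledge that visible parent entry may partly unblind the review. Do not base the final seizure classification on truncated clips, since the reviewer must identify tonic seizures lasting more than 30 seconds.

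**Cost.** One additional set of results. With 10-minute windows and 10-hour nights (both assumptions), 864 × 10 / 60 = 144 hours out of 3,600 × 10 = 36,000 hours leave the restricted analysis, about 0.4%.

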#### **Questionnaires & interviews**

During the study (T0 and T2), parent(s)/guardian(s) will be asked to complete several questionnaires about their experiences with NightWatch, quality of life, stress and quality of sleep. This will take 40 minutes for each time period (T0 and T2). The questionnaires will be presented in an online tool. Parent(s)/guardian(s) will give their consent to use their email address for access to this tool. A subgroup of parent(s)/guardian(s) will be invited to participate in a semi-structured interview focusing on feasibility of NightWatch and the impact of the SDD on family life. This interview will take one hour. Parent(s)/guardian(s) can indicate their availability to participate on the informed consent form. Based on all evaluations, researchers will decide which perspective will gain deeper understanding about the feasibility and impact of NightWatch. The researchers will select parents/guardians based on maximum variation.

#### **Optional phase**

Depending on the performance of NightWatch, parent(s)/guardian(s) will have different options. In case of bad performance, the researchers will offer them a second-2-month period of monitoring if an individually tailored adjustment of the algorithm could substantially improve performance. In case of good performance.

researchers we will offer the parent(s)/guardian(s) the possibility to keepNightWatch for further use. They can buy NightWatch at a 50% reduced rate of €750,-.

# 8.4 Withdrawal of individual subjects

Subjects can terminate the study at any time for any reason if they wish to do so without any consequences. The investigator can decide to withdraw a subject from the study for urgent medical reasons or important unforeseen events (e.g. material deficiencies). If the subject shows any signs of resistance to wear the device, the investigators are obliged to withdraw the subject from the study.

Researchers will ask for the reason of withdrawal, because this can give them information about the feasibility. Subjects and their parent(s)/representative(s) are not obliged to answer this question.

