# 4.4 Sample size calculation

If 60 subjects are monitored for two months at minimal seizure frequency of 1 per week we will likely obtain around 540 seizures. To assess the diagnostic performance of the NightWatch this sample size seems sufficient. The detection algorithms aim to reach a sensitivity of 80% and a PPV of 50%. A sample size of 384 would be sufficient to reach a confidential interval of 5% (given a confidence level of 95%) [24]. A sample size of 60 subjects will allow us to intercept a drop-out rate of approximately 30% for the feasibility study.

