#### 8.4.1 Specific criteria for withdrawal (if applicable)

#### 8.5 Replacement of individual subjects after withdrawal

If a subject is withdrawn from the study within two weeks from inclusion, the subject will be replaced. After this time period, subjects will not be replaced.

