# 8.6 Follow-up of subjects withdrawn from treatment

Not applicable.

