#### 10.2 Secondary study parameter(s)

Methods triangulation will be conducted for this study, which means that there will be two or more research methods applied in one study [30,31]. After analysis the results will be combined, leading to a deeper understanding concerning the feasibility parameters.

Feasibility and utility of the NightWatch will be presented, using descriptive statistics (see table 3). To calculate differences in pre- and post-measurements, a paired samples T-test will be applied (in case of normal distribution). Multiple imputation test will be applied in case of missing data. Differences in outcome will be tested through a post-hoc test.

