#### **Group session**

A focus group session with subjects, parents/guardians and professionals will be organized. After consent of the participants, the session will be recorded on video and transcribed verbatim will be used for further thematic analysis.

Table 3. Analysis for feasibility parameters

Feasibility parameter	Source	Analysis
Acceptability		
Satisfaction	- Survey T2	- Descriptive statistics 
	- Interview	- Thematic analysis
Intent to continue use	- Survey T0	- Descriptive statistics 
	- Interview	- Thematic analysis
Expectations	- Survey T0	- Descriptive statistics 
Demand		
Actual use	- Diary	- Descriptive statistics 
	- Interview	- Thematic analysis
Perceived demand	- Survey T0	- Descriptive statistics 
	- Survey T2	- Descriptive statistics 
Implementation		
Degree of execution	- Diary	- Descriptive statistics 
	- Interview	- Thematic analysis
	- Survey T2	- Descriptive statistics 
Success or failure of execution	- Interview	- Thematic analysis
	- Survey T2	- Descriptive statistics 
Amount, type of resources needed to	- Interview	- Thematic analysis
implement		
Practicality		
Factors affecting implementation ease or	- Interview	- Thematic analysis
difficulty	- Survey T2	- Descriptive statistics 
Positive/negative effects on people with	- Interview	- Thematic analysis
epilepsy and their family members	- Survey T2	- Descriptive statistics 
Ability of parents/guardians to carry out	- Interview	- Thematic analysis
intervention activities	- Survey T2	- Descriptive statistics 
Expansion		
Fit with organizational goals and culture	- Group session	- Videotaped and thematic analysis
treatment of people with epilepsy		
Disruption due to expansion component	- Group session	- Videotaped and thematic analysis
	- Interview neurologist	- Thematic analysis
Limited-efficacy testing		
Health-related QoL	- EQ-5D-5L	- Check on normally distributed data
		- Descriptive statistics 
		- Paired samples T-test
Caregiver Strain Index (CSI)	- CSI	- Check on normally distributed data
		- Descriptive statistics 
		- Paired samples T-test
Pittsburgh Sleep quality index (PSQI)	- PSQI	- Descriptive statistics 

- Repeated measures ANOVA (if necessary multiple imputation)
- post-hoc test (Turkey's HSD)

- 1 = Median, mode, range, highest and lowest value

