#### 12 STRUCTURED RISK ANALYSIS

#### 12.1 Potential issues of concern

# 12.2 Synthesis

Implementation of our wearable sensor device (NightWatch) is not considered to pose any substantial risk. Since the efficacy of NightWatch has not yet been proven in children in a family home setting, we cannot guarantee that subjects and parents/guardians can rely completely on this device. There is a chance that parent(s)/guardian(s) will become less alert during the study. To minimize this risk, we will give them extensive information that especially emphasizes this matter.

Study participation can be a burden for the family, due to the impact of the devices on their privacy, the impact of false alarms and the time spend on completing questionnaires, interviews and a diary. It does, however, also give the families better insight in seizure behavior of their child and shows them the possible utility of seizure detection.

If the NightWatch becomes uncomfortable or causes any distress, the wearable device will be removed and the subject will be withdrawn from the study. In case of alarm fatigue, the parents/guardians can stop the NightWatch measurements and contact the researcher to switch off the alarms. If the subject or parents/guardians wish(es) to stop the video registration for any reason, they can contact the researchers to switch off the video recordings or even all recordings.

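### Families withdrawn because the child resists the device have no T2 scores, so the T0–T2 change describes only families who kept using it

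*Combined protocol and SAP*

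**What the plan says.** On a child who does not accept the device, section 8.4 says: "If the subject shows any signs of resistance to wear the device, the investigators are obliged to withdraw the subject from the study". Section 12.2 repeats this for discomfort: "If the NightWatch becomes uncomfortable or causes any distress, the wearable device will be removed and the subject will be withdrawn from the study". Section 11.3 also covers a device that is a nuisance, but speaks only of taking it off in consultation with the parents and does not mention leaving the study. The section headed "8.6 Follow-up of subjects withdrawn from treatment" is entered as not applicable.

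These families are not replaced. Replacement is limited to withdrawals within two weeks of inclusion (8.5: "After this time period, subjects will not be replaced"), and the device arrives later than that (8.3, Intervention: "After two months, the researcher will visit the home to install the equipment").

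CSI, PSQI and EQ-5D-5L are collected at T0 and T2 only (8.1.2 and Table 1). Section 10.2 plans a paired t-test and adds: "Multiple imputation test will be applied in case of missing data". Table 3 mentions imputation once more, as "Repeated measures ANOVA (if necessary multiple imputation", apparently in the PSQI row. Neither place gives an imputation model, a missing-data assumption or a sensitivity analysis. Section 10.3 derives QALYs from EuroQol scores and names no method for missing data. Section 4.4 allows for "a drop-out rate of approximately 30% for the feasibility study".

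**The concern.** The T2 score is lost because of the thing being evaluated: the family stops because the child does not tolerate the device. Followed as written, the plan yields no T2 score from any such family, so the data cannot show how these families changed. An imputation model that conditions on T0 has only the remaining families to learn from.

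At stake are the limited-efficacy outcomes (strain, sleep, quality of life) and the cost-utility analysis built on EQ-5D-5L. A T0–T2 change reported for all enrolled families would in fact be the change among those who kept the device. Post-withdrawal T2 scores cannot be recovered once the trial has ended.

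**Working it through.** **1. The plan's own figures.** In 4.4, 384 seizures follows from 1.96² × 0.5 × 0.5 / 0.05² = 384.1, and 540 follows from 60 children × 9 weeks × 1 seizure. Both concern diagnostic performance. For the feasibility outcomes, 4.4 gives only 60 subjects and about 30% drop-out: 60 × 0.70 = 42 completers and 18 lost. No effect size, SD or power is stated for CSI, PSQI or EQ-5D-5L, so nothing more can be reproduced.

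**2. Formula.** Let g be the mean change in completers, h the mean change in families withdrawn because of the device, and d their share.

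- Mean change over all families: (1 − d)g + dh.
- Estimate from completers, or from a standard imputation fitted to them: about g.
- Error: g − [(1 − d)g + dh] = d(g − h).
- With h = 0, relative overstatement: g / [(1 − d)g] − 1 = 1/(1 − d) − 1.

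| d | Families of 60 | Calculation | Overstatement |
|---|---|---|---|
| 10% | 6 | 1/0.90 − 1 | 11% |
| 20% | 12 | 1/0.80 − 1 | 25% |
| 30% | 18 | 1/0.70 − 1 | 43% |

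**3. Simulation check.** The set-up was 60 families, T2 regressed on T0 in completers, 30 imputations combined by Rubin's rules, and 1,500 trials per scenario. Three assumptions are not in the documents: a T0–T2 correlation of 0.5, a completers' change of ±0.5 SD or zero, and zero change in withdrawn families. Results are mean change in SD units, with positive meaning improvement.

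| Scenario | All 60 followed up | Completers only | Multiple imputation |
|---|---|---|---|
| 10% withdrawn, completers +0.5 | 0.447 | 0.497 | 0.497 |
| 20% withdrawn, completers +0.5 | 0.397 | 0.496 | 0.496 |
| 30% withdrawn, completers +0.5 | 0.352 | 0.504 | 0.505 |
| 30% withdrawn, completers −0.5 | −0.348 | −0.494 | −0.494 |
| 30% withdrawn, no change in either group | −0.004 | −0.001 | −0.003 |

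In the third scenario a two-sided 5% test rejects in 75% of trials with full follow-up, 89% with completers only and 91% with imputation. The all-family mean is truly above zero there, so this is overstated strength of evidence, not a false-positive rate. In the last scenario the rejection rates are 5.7%, 5.7% and 5.3%, so there is no inflation.

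The completer-only and imputation columns agree throughout. The error comes from losing T2 at withdrawal, and omitting imputation does not remove it.

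**The case against.** A reader might infer more than the documents support, in four ways.

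- **That the plan imputes T2 from completers.** No such rule is written; 10.2 leaves the model open. It is the default result when no withdrawn family supplies a T2 score.
- **That the result is biased in favour of NightWatch.** With unchanged withdrawn families, this holds only if completers improve. Sections 11.4 and 12.2 expect burden from false alarms and loss of privacy. If completers worsen, their worsening is overstated instead.
- **That 43% is the expected size.** The 30% in 4.4 is not split by cause, and 9.2.2 reports that earlier trials found the device well tolerated. The device-related share may be small.
- **That withdrawn families should be set to zero change in the main analysis.** The comparison is an uncontrolled before-after one, so withdrawn families may share time trends or regression to the mean, and zero is not known to be their true change. Entering T0 as if it were an observed T2 also understates uncertainty.

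It can also be said that intolerance is captured elsewhere, through withdrawal reasons (8.4), retention rate (section 3), hours of use (8.1.2) and interviews (8.3). An effect among users is a legitimate target for a secondary, limited-efficacy outcome. The entry in 8.6 may be template filling, since chapter 5 on treatment is marked the same way.

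These points narrow the concern but do not remove it. Giving a withdrawal reason is optional, retention is taken from a survey after the exposure period, and interviews cover a subgroup; none of these is linked to the T0–T2 analysis. If users are the target, the plan does not say so. Nor does any section provide for T2 scores from withdrawn families.

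**Conclusion.** The point holds as a gap in data collection and in the stated target of the T0–T2 analysis. The absolute error is d(g − h), which is zero if neither group changes. With no change in withdrawn families, the completers' change in either direction is overstated by 11%, 25% or 43% at d = 10%, 20% or 30%. The value of d is unknown, and 43% needs the whole planned drop-out to be device-related. It is an upper illustration with respect to d only: if completers gain and withdrawn families worsen, the error at a given d is larger. Families who have the alarms switched off but stay in the study (11.4) can still give T2 scores and are not part of the problem. The primary diagnostic endpoints are not addressed by this point. The outcomes are secondary, but the repair is cheap and must be in place before families leave, so the change should be made.

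**What to change.** No change to the withdrawal rule is proposed. Sections 8.4 and 12.2 (withdrawal from the study) and 11.3 (device removed, withdrawal not mentioned) must be reconciled, because the difference determines how many T2 scores are lost.

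- **8.4 and 8.6:** invite parents of withdrawn children to complete the existing online T2 questionnaires voluntarily at the scheduled T2 time (about 40 minutes, per 8.3).
- **10.2 and 10.3:** use these scores in the analysis, and state the imputation model and which families the T0–T2 effect is meant to describe.
- **Where T2 is still missing after a device-related withdrawal:** keep multiple imputation and report beside it a sensitivity analysis for CSI, PSQI, EQ-5D-5L and QALYs. This should assume no change from T0, or use a delta-adjusted range. The no-change version is better run as an imputation centred on zero change than by entering T0 as an observed value.
- **Reporting:** if no post-withdrawal scores are obtained, say that the T0–T2 effect describes families who kept using the device.

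The cost is some protocol and analysis wording, one optional questionnaire round for families who have left, a little more analysis, and possibly a less favourable estimate.
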